Cambridge Neuropsychological Test Automated Battery (CANTAB) (at screening or baseline, week 6 and week 12): CANTAB is a computer-based system designed to look at frontal lobe (executive functioning). Select subtests will include the following:

- Spatial Working Memory (SWM), tests comprehension, learning and reversal.
- Stockings of Cambridge (SOC), assesses spatial planning and motor control.
- Intra-Extra Dimensional Set Shifting (IED), tests rule acquisition and attentional set shifting.
- Reaction Time (RTI), measures speed of response.
- Rapid Visual Information Processing (RVP), tests sustained visual attention.
- Affective Go/No-go (AGN) assesses information-processing biases for positive and negative stimuli.
- Verbal Recognition Memory (VRM), assesses immediate free recall, and immediate and delayed recognition memory
- Cambridge Gambling task (CGT), to assess decision-making and risk-taking behavior.

Clinician rated assessments (rated at each in-office study visit, unless otherwise noted):

- Global Assessment of Functioning (GAF) scale. The GAF will assess global functioning using a scale from 1 (worst) to 100 (best). This will be collected at all study visits, excluding the screening visit.
- Clinical Global Impressions (CGI) scale for ADHD. The CGI is a measure of illness severity, improvement, and efficacy of treatment.
- Adult ADHD Investigator Symptom Rating Scale (AISRS). Each of the individual symptoms of ADHD is rated 0 to 3 on a scale of severity.
- Adverse Experiences (collected at all visits excluding the screening and baseline visits) and Concomitant Medications.

Subject rated scales (all scales rated at baseline, week 6, and week 12 or drop visit, unless otherwise noted):

- The 18-item ADHD Self Report Rating Scale (ASRS) to evaluate frequency of ADHD symptoms on a scale of 0 to 4.
- The 86-item Behavior Rating Inventory of Executive Function Adult Form (BRIEF-A) to assess levels of executive function deficits. ³⁶ This will be collected at baseline and at Week 12.
- The Adult Self-Report Form (ASR) to measure a wide range of psychiatric syndromes (i.e., depressive problems, anxiety problems, antisocial personality problems) in adults. The ASR provides dimensional scale scores for each syndrome that are age- and gender-normed. ³⁷
- The 16-itm Quality of Life Enjoyment & Satisfaction Questionnaire (Q-LES-Q) to measure overall satisfaction across different aspects of daily life. ³⁸
- The 25-item Endicott Work Productivity Scale (EWPS) to measure behaviors and feelings likely to reduce productivity and efficiency in work activities. ³⁹

Data Collection:

Self-report and clinician-rated measures will be collected using DatStat IllumeTM, a platform for electronic data capture that streamlines data collection and management, and ensures data integrity, resulting in improved data quality. The DatStatTM software allows researchers to design and implement study surveys for collecting, storing, retrieving, and manipulating data electronically. Participants and/or research staff enter survey responses into electronic assessment forms, and the responses are then transmitted securely via encrypted connection and stored in a secured database. This electronic data capture obviates the need for subsequent data entry by staff, thus minimizing human error. Efforts will be made to have all surveys completed in-office, but if needed participants may complete them from home.

Survey respondents will log in to the secure data-collection system at the study site, on a desktop computer provided by MGH staff, or from home, using a personal computer with Internet access. All responses will be transmitted to and stored in a secure database via an encrypted connection. This electronic data capture system obviates the need for the physical transportation of paper source data as well as the entry of paper source data by staff, thus minimizing human error. All data collected via DatStatTM are immediately available for analysis by a statistical package.

All collected data are stored automatically and securely on a Microsoft SQL Server, accessed over an industry standard SSL 128 bit RSA encrypted connection during data transfers. Data is routinely backed up locally onto a redundancy server and stored in a separate database. Individual computers designated for data capture do not store participants' identifying information nor study data. All collected data will be systematically checked by the Project Coordinator.

In the event that the electronic data capture system is unavailable during a study visit (due to technical issues), rating scales will be collected on paper and then entered into the program manually once the system becomes available.

The DatStat Illume[™] and Discovery[™] Electronic Data Capture Platform has been approved for use at Massachusetts General Hospital by Partners Health Care System Research Computing, Enterprise Research Infrastructure and Services (ERIS) Department. The data collection, transmission, and storage methods are secure and in compliance with Partners policies and procedures. In addition, it is in compliance with the HIPPA HITECH ACT because data is hosted and stored internally (PHS IS Data Center) and managed by Partners Employees.

For quality control purposes, clinician-administered measures completed during the visits may be audio taped, with subjects' permission. These recordings will be used to monitor quality control and inter-rater reliability in this study by the PI. Each digital audio file will be coded with subject initials and number to maintain confidentiality. These files will be de-identified and stored on a password-protected, encrypted computer within the Partners firewall, and will be accessed only by the appropriate study staff.

Study Completion:

Upon completion of the study, participants can choose to pursue follow-up care, as possible, at our MGH practice or continue treatment with their primary care physician. Study clinicians may also offer psychiatric referrals to treaters in their communities. All subjects will be offered two free follow-up visits in the clinic.

ADHD Pharmacotherapy:

If a subject enters the study on pharmacotherapy for ADHD, they will be maintained on this agent during the study by a study clinician, and will receive L-Threonic acid Magnesium salt in addition. With

written permission of the subject, prior to beginning the study, subjects' treaters will be contacted by mail (followed by a phone call) before the study clinician initiates treatment.

Subjects who are not on pharmacotherapy for ADHD as they enter the study will take only L-Threonic acid Magnesium salt during the study. No individual will be removed from an effective and stable treatment regimen for the purposes of participating in the study.

Those subjects who are treated for ADHD prior to their enrollment in the study will continue to be responsible for the cost of their medication, as they will be instructed to take this medication as usual. The study drug will be provided at no cost to study participants.

Study Agent and Dosing:

L-Threonic acid Magnesium salt will be provided as MMFS202 (6-hour release) and MMFS302 (12-hour release). Neurocentria, the makers of MMFS202 (6-hour release) and MMFS302 (12-hour release), will provide a detailed Certificate of Analysis attesting to the contents of the product.

Neurocentria-has provided the following list of ingredients for MMFS202 (6-hour release) and MMFS302 (12-hour release):

- Inactive ingredients: polyvinyl pyrolidone, microcrystalline cellulose, silicon dioxide, talc, and magnesium stearate

Both MMFS202 (6-hour release) and MMFS302 (12-hour release) will be provided in 0.5-gram tablets. Participants will be instructed to take one tablet of MMFS302 (12-hour release) in the morning and one tablet of MMFS202 (6-hour release) in the evening for one week 2 hours before bedtime. After one week, if well tolerated subjects will start a regimen of two tablets of MMFS302 (12-hour release) in the morning and two of MMFS202 (6-hour release) in the evening. Therefore, subjects will take up to 2 grams per day of L-Threonic acid Magnesium salt during the course of the study. However, study agent dosing will be flexible. If individual subjects display patterns of adverse effects or drug effects that suggest an alternative dosing schedule would be preferred, this will be allowed, including dose reduction to only one of either MMFS202 (6-hour release) or MMFS302 (12-hour release). The study clinician can increase or decrease the dose based on tolerability and reinstate higher doses after a decrease if tolerability increases. No subject will take more than two MMFS202 (6-hour release) or more than two tablets at a time or to take more than four tablets in a day total. Subjects will be encouraged to spread out the daily dose into at least two doses several hours apart.

This approach to dosing will allow us the flexibility to maintain subject comfort and convenience during study participation.

The active ingredient in MMFS202 (6-hour release) and MMFS302 (12-hour release), L-Threonic acid Magnesium salt has been granted GRAS status by the FDA. Neurocentria produces MMFS202 (6-hour release) and MMFS302 (12-hour release) using good manufacturing practices.

Study clinicians, or research assistants under the supervision of a study clinician, will be responsible for dispensing MMFS302 (12-hour release) and MMFS202 (6-hour release) at our research office. The MGH Clinical Trials Pharmacy will receive and label and distribute the product for dispensing during the study.

Study clinicians, in cooperation with the subject and the subject's treater, may develop a plan for continued MMF302 (12-hour release) and MMF202 (6-hour release) treatment after the completion of the study, if appropriate. At each visit, measures of safety and effectiveness will be administered and subjects will be evaluated for response and side effects to the treatment. To assess and increase adherence to dosing of the agent, the study agent and any concurrent ADHD medication treatment will be returned and counted at office visits.

Concomitant Medications / Treatments:

A detailed past and present treatment history will be taken as part of initial screening. Concomitant medications with primarily central nervous system activity, other than ADHD pharmacotherapy as noted above, are not allowed in this study. No subject will be tapered from medication that is useful to him or her. Non-pharmacological treatments such as individual, family or group therapy will be allowed if they were in place before the patient joined the study. Any such therapy regimen must remain the same throughout the study. If a subject is asked to stop a medication with central nervous system activity for participation in the study, sufficient time will pass off the medication prior to baseline visit, based on the pharmacokinetics of the agent, to ensure that it has been eliminated from the patient's system.

Subjects will be instructed not to take any medications or supplements that contain any forms of magnesium compounds to avoid unsafe levels of magnesium. All new medications and supplements started during the study will be reviewed by the PI, and subjects may be dropped from study participation, but their data will be retained in the safety and intent-to-treat analyses with PI discretion.

In addition, any subject found to be taking medication listed as exclusionary during the course of the study or the seven days prior to baseline will be evaluated by the PI for ongoing eligibility.

Study Discontinuation Criteria

Subjects who: 1) develop intolerable AE(s) despite dose adjustments; 2) have (a) clinically relevant serious AE(s) as determined by the investigator; 3) have worsening ADHD symptoms (much worse or very much worse as rated on CGI-Improvement at two consecutive visits); or 4) have emergent adverse mental health state including psychosis, suicidality, substance use, or worsening mood and/or anxiety; 5) are non-adherent to study procedures or withdraw from the study; 6) intend to be or become pregnant will no longer continue in the study. If study participation is discontinued due to safety reasons, participants will receive two follow-up visits, giving adequate time for appropriate psychiatric referrals to treaters in their communities.

Subjects found to be taking substances listed as exclusionary during the course of the study may be discontinued based on PI evaluation of their eligibility.

VI. BIOSTATISTICAL ANALYSIS

As this is a single-arm, open study designed to evaluate the effectiveness and safety/tolerability of L-Threonic acid Magnesium salt, formal power analyses are not warranted.

Data processing and management will follow procedures developed by the investigators and used in ongoing studies. 15 subjects will receive L-Threonic acid Magnesium salt. Changes in outcome ratings within and between study groups will be tested. All analyses will be intention to treat (ITT), utilizing.

Our exploratory hypotheses are as follows. Our primary test of Hypothesis 1 will be review of the occurrence of moderate or severe adverse events. Hypothesis 2 will be tested by evaluating whether over the course of L-Threonic acid Magnesium salt administration the following are seen: a) at least a 25% reduction in ADHD as rated by the AISRS total score; b) CGI of much or very much improved, c) reduced symptoms of executive dysfunction (defined by a 0.5 standard deviation improvement on BRIEF-A self-report total or subscale scores). Hypothesis 3 predicts that there will be measurable improvement in cognitive function, as

measured by a) statistically significant improvement on CANTAB tasks, and b) improvement in performance on the WASI matrix, used to estimate IQ, and c) increased correlation between performance on domains of function.

For ADHD AISRS, BRIEF, and CANTAB evaluations, we will compare pre-treatment and study visit values of measures using paired t-tests, via an intention-to-treat analysis with the last observation carried forward (LOCF) for subjects who did not complete the full study. Alpha will be set at 0.05 for all comparisons.

We will also explore descriptively whether baseline erythrocyte magnesium level, or deficits in BRIEF or CANTAB ratings as measured against norms predict improvement on AISRS or BRIEF ratings.

VII. RISKS AND DISCOMFORTS

All efforts are made to minimize risks to subjects. Consistent with good clinical practice, safety will be monitored by the Principal Investigator, and will reflect the oversight of co-investigator study clinicians. Adverse events will be recorded and reported according to institutional policies. Risks of the study agent have been incorporated into the exclusionary criteria for this proposal.

Study clinician evaluation and subject questionnaires:

Some questions may make subjects feel uncomfortable. Subjects may refuse to answer any question they wish. In the event that a participant reports risk of harm to himself or herself, or to another person, study clinicians will assess the level of risk, and take appropriate actions, including disposition of an immediate referral to a local Psychiatric Emergency Room.

Study Agents –MMF202 (6-hour release) and MMF303 (12-hour release):

The active ingredient in MMF202 (6-hour release) and MMF303 (12-hour release) is L-Threonic acid Magnesium salt, is considered a dietary supplement that the manufacturer has self-certified as fulfilling the US Food and Drug Administration criteria for agents that are Generally Regarded as Safe. There are few risks to taking L-Threonic acid Magnesium salt orally. Magnesium is known to cause gastrointestinal discomfort, nausea, vomiting, or diarrhea. Although occurrences are rare, very large amounts of magnesium might cause hypermagnesemia with symptoms including thirst, hypotension, drowsiness, confusion, loss of tendon reflexes, muscle weakness, respiratory depression, cardiac arrhythmias, coma, cardiac arrest, and death. There have been only two reports of death from hypermagnesemia that we found record of. ⁴³ The dose prescribed to subjects as part of this study will unlikely lead to hypermagnesemia, as extremely high doses of magnesium are required to produce this effect.

ADHD Pharmacotherapies:

Some individuals will enter the study taking medication for ADHD and continue in the study on this medication. Only subjects taking FDA approved agents for treatment of ADHD in adults (stimulants-class medication or Atomoxetine) will be enrolled. The risks to these subjects are not expected to change with the addition of L-Threonic acid Magnesium salt to their treatment regimen.

Commonly observed side effects associated with the use of these FDA-approved stimulants include insomnia, decreased appetite, dry mouth, headache, or increased pulse. Other less common side effects include irritability, stomach pain, onset of tics, or mood changes. Stimulants have also been associated with more rare, but serious, adverse effects such as sudden death, stroke, and heart attack in adults with a history of heart disease.

Side effects of Atomoxetine are similar to those of stimulants, but notably include fatigue, nausea, increase in heart rate, increase in blood pressure, sexual side effects, agitation or changes in mood. The label for Atomoxetine carries warnings about rare reports of liver failure and of suicidal ideation. Subjects receiving ADHD pharmacotherapy prior to trial entry will continue their regimen as usual, with treatment managed by the study clinicians.

Washout:

During the washout period, if the subject stops taking his/her medications, his/her symptoms might get worse. Medication washout will be monitored by the study clinician in agreement with the research subject and in consultation with the prescribing physician. No subject will be removed from a stable and effective treatment regimen for the purposes of participating in the study. All medications that are discontinued for the purpose of enrollment will be thoroughly documented, and the PI will regularly evaluate the subject's status off the drug and document any subsequent adverse events. This will be done at Week 0, 6, and 12, although all adverse events will be documented throughout the study, including any relation to medication washout. If the investigator determines that it would be beneficial to the subject to resume their previous medication, they will be withdrawn form the study and referred for clinical care.

Confidentiality:

All research-related records initiated as a result of a subject's participation in this study that reveal the subject's identity will remain confidential except as may be required by law. Results of urine drug or pregnancy testing will not become part of the subject's medical record. The result of the magnesium and calcium blood test may be be entered in the subject's hospital medical record, as Medical Record Numbers may be used by the laboratory to identify samples. This will be explained in the Consent Form so that all subjects are made aware of this.

Information regarding communication with subject's other treater(s) will be explained explicitly in the Consent Form. Should a subject be opposed to study staff communicating with subject's treaters, he/she may refuse consent to participate in the study. Data obtained from this study will not identify the subjects individually. Subjects will be assigned code-names and ID numbers. Data obtained from our studies may be published, but no subjects will be identified individually in these publications. Original research-related records may be reviewed by the Partners Human Research Committee, and regulatory authorities, for the purpose of verifying clinical trial procedures and/or data. Information may be held and processed on a computer. Access to these computerized records will be password protected and restricted to study staff. Subjects will only be contacted regarding future studies if they indicate that they are interested in being contacted by initialing in the specific section of the consent form.

VIII. POTENTIAL BENEFITS

There may be no direct benefit to subjects participating in this study. Potential benefits to the participants include education about ADHD, a trial of a supplement that could be continued after the study, and the opportunity to contribute to medical science and thus help others with similar difficulties.

IX. DATA AND SAFETY MONITORING

At each study visit, the interviewing clinician will evaluate the appropriateness of a subject's continued participation based on presence and severity of adverse events. The study Principle Investigator will review all adverse events that have occurred across all subjects of the study at least monthly to determine if there are

concerning trends in participants' experience that would require discontinuation of study participation or modification of the protocol. The Principal Investigator will confirm that all adverse events are correctly entered into the adverse event log by the coordinator and will be available to answer any questions that the coordinators may have concerning adverse events and notifying the IRB of all serious adverse events and adverse events in accordance with the guidelines outlined on the Partners Human Research Committee web site.

The Principal Investigator will meet regularly with study staff to address procedural issues and the study coordinator will audit each subject's data within 48 hours of each study visit. Furthermore, all data will be audited by the study statistician on a regular basis to ensure the progress of the study and confirm that all necessary data is being collected and can be transitioned to the statistical package smoothly. Co-investigators are actively involved in the monitoring and quality assurance of these trials. Periodic quality assurance audits will insure accuracy and completeness of all subject documents, IRB files and correspondence, and the informed consent documentation.

	Screen	Baseline (Week 0)	Week 1	Week 2	Week 3	Week 4	Week 5	Week 6	Week 7	Week 8	Week 9	Week 10	Week 11	Week 12 (Drop)
Consent	Х													
Eligibility	Х	X ^a												
Procedures														
Blood Pressure	Х	Х			Х			Х			Х			Х
Pulse	Х	X X			X			X X			Х			Х
Weight	Х	Х			Х			Х			Х			Х
EKG	Х													Х
Height	Х													X
RBC Mg and Calcium	Х													Х
Urine Drug	Х							Х						Х
Urine Pregnancy	X							Х						Х
Drug accountability		X ^b			Х			Х			Х			Х
Drug Dispensing		Х			Х			Х			Х			
Phone Contact			X ^c	Х		Х	Х		Х	Х		X	X	
Assessments														
Demographic Interview	Х													
WASI-II	Xd	Xď												Х
D-KEFS Trails	X ^d	X ^d						Х						Х

VIII. Visual Timeline of Key Study Elements

CANTAB	X ^d	Xď				X					Х
Clinician Evaluation	X										
Clinician Rated Scales											
AISRS	Х	Х		Х		X		X			Х
CGIs	Х	Х		X		Х		X			Х
GAF		Х		X		Х		X			Х
Adverse Events			Х	X		X		X			X
Concomitant Medications	X	Х		X		X		X			Х
Subject Rated Scales											
BRIEF-A		Х									Х
ASRS		Х		X		Х		X			Х
ASR		Х									Х
Q-LES-Q		Х									Х
EWPS		Х									Х

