Preclinical studies suggest that L-Threonic acid Magnesium salt can modulate rat brain function. Slutsky, et al (2010) demonstrated that oral delivery of L-Threonic acid Magnesium salt to rats achieves significantly higher levels than the control feed, whereas magnesium chloride, magnesium orotate, or magnesium gluconate did not. This report also demonstrated increases in synaptic density in hippocampal regions, and reversed task impairment in Alzheimer's-model rodents. Therefore, L-Threonic acid Magnesium salt could be expected to have central nervous system effects in human subjects, including potentially alleviation of ADHD symptoms.²³

The risk profile of magnesium supplementation is favorable relative to that of pharmaceuticals currently available under FDA indication for Attention Deficit Hyperactivity Disorder. In a rat model, magnesium chloride at an intake of up to 2.5% of food resulted in no significant toxic effects. ³⁰ In addition, acute and chronic supplementation for hypomagnesemia has been well tolerated with a favorable safety profile. ^{31, 32}

Magnesium supplements, including L-Threonic acid Magnesium salt, are widely purchased and consumed. The most common side effect of magnesium supplementation may be diarrheic effects. Neurocentria, the makers of the study agent MMFS202 6-hour release and MMFS302 12-hour release, has communicated that in preliminary studies they have not found significant side-effects with 2 g/day of L-Threonic acid Magnesium salt.³³ Some subjects reported sleepiness, but it subsided after a few days. There were also some reports of vivid dreams and restlessness.³⁴

Conventional therapies for ADHD are thought to work in part through reuptake blockade and/or increased release of the catecholamines dopamine and norepinephrine. ¹³ L-Threonic acid Magnesium salt, therefore, offers a novel mechanism of modulating cognitive function. If effective and well tolerated, it could offer a novel modality for support of ADHD or related cognitive deficits.

Because L-Threonic acid Magnesium salt could have positive effects on ADHD symptoms, it has not yet been evaluated in adults with ADHD, and is expected to be well tolerated, we propose to conduct an open-label pilot study enrolling 15 adults with ADHD to receive L-Threonic acid Magnesium salt. The study is designed to evaluate tolerability and feasibility of the protocol, and guide development of future more definitive doubleblind study of the selected outcomes.

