Informed consent will be obtained prior to the performance of any protocol procedures and prior to administration of study drug. The informed consent document will be used to explain in simple terms the risks and benefits of study participation to the subject. The nature of the study will be fully explained to the subject by a board-certified physician who is either the primary investigator or a co-investigator. The subject will be encouraged to ask questions pertaining to their participation in the study and the subject may take as much time as they feel is necessary to consider his/her participation in the study as well as consult with family members or their physicians. Participation in this study is voluntary and the subjects may withdraw from the study at any time. The IRB-approved informed consent documents will be signed and dated by the subject and the physician obtaining consent.

V. STUDY PROCEDURES

We will conduct a 12-week open label pilot clinical trial exploring the cognitive effects and tolerability of L-Threonic acid Magnesium salt in adults with ADHD. We will recruit up to 25 subjects, and enrollment will stop once 15 subjects are expected to complete the study.

After providing study information and obtaining IRB approved informed consent, participants will undergo a comprehensive assessment including a psychiatric assessment reviewing current and lifetime DSM-V Axis I conditions, medical history including history of any cardiac symptoms or abnormalities reported on routine clinical exams, and a neuropsychological evaluation which will include confirmation of an IQ greater than 80 (which can be completed at the screening or baseline visit for scheduling flexibility). If a subject has never had a cardiac physical exam a clinician will conduct one. The information obtained at this visit will be reviewed to assure that all inclusion and exclusion criteria are met prior to receiving study agent at the baseline visit. Subjects who do not meet all the criteria for enrollment after these assessments will be discontinued.

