Vital signs (blood pressure, pulse, weight) will be measured at every in-office visit. Height will be measured at baseline and at the end of the study. A urine drug screen will be performed at screening, week 6, and week 12. If the participant is found to have taken an illicit drug, he/she will have a discussion with the doctor to determine if he/she can be in the study. Subjects will be discontinued if there is suspicion of ongoing substance use. For safety purposes, an EKG will be conducted during screening and at the endpoint of the study. Females who are able to have children will also have a urine pregnancy test at screening, week 6, and week 12.

If a participant has a positive pregnancy test she will not be able to take part in the study. Female subjects of childbearing potential must agree to use a medically acceptable form of birth control (such as male for female condoms with or without spermicidal agent, diaphragm or cervical cap with spermicide, medically prescribed IUD, hormonal contraceptives like birth control pills, or abstinence) while they are receiving study agent and for 1 month after the last dose of study agent. In the event that a subject becomes pregnant, we will ask the subject's permission to obtain information about the outcome of the pregnancy and the condition of the newborn. Those subjects who terminate study participation before the completion of the study will be asked to complete all tasks scheduled to take place on the final study visit at the time of study discontinuation.

We will draw blood samples at the screening visit and at study endpoint to determine erythrocyte (red blood cell or RBC) levels of magnesium and calcium. Samples will be analyzed by LabCorp through services provided by the Harvard Clinical and Translational Science Center. Each sample volume will be approximately 3 teaspoons, for a total of 6 teaspoons drawn over the entire study.

All efforts will be made to protect subject privacy, and samples will be labeled with codenames and medical record numbers. The sponsor will not have access to information that identifies participants' samples. Results from laboratory testing (i.e. laboratory values) may become a part of the subjects' MGH medical records, however no information regarding participation in the study will become a part of the medical record.

Subject Visits:

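### Non-adherence ends all observation, so an analysis called intention to treat carries forward an exit value where a week 12 outcome could have been collected

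*Combined protocol and SAP*

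**What the plan says.** Under V, Study Discontinuation Criteria, the fifth and sixth grounds cover subjects who "are non-adherent to study procedures or withdraw from the study; 6) intend to be or become pregnant will no longer continue in the study". The only consequence named is leaving the study. There is no separate provision for stopping the agent while ratings continue, and non-adherence is not defined. The last sentence under Medication Washout likewise lets participation run for 12 weeks or until it is ended.

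Section VI states: "All analyses will be intention to treat (ITT), utilizing" (the sentence ends there in the public text). For AISRS, BRIEF and CANTAB it adds paired t-tests "via an intention-to-treat analysis with the last observation carried forward (LOCF) for subjects who did not complete the full study".

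Under Safety Assessments, subjects who leave early "will be asked to complete all tasks scheduled to take place on the final study visit at the time of study discontinuation". The timeline gives this visit the same column as week 12. Contact after exit is limited:
- Study Discontinuation Criteria: "If study participation is discontinued due to safety reasons, participants will receive two follow-up visits". The stated purpose is referral.
- Study Completion: "All subjects will be offered two free follow-up visits in the clinic". No study measure is listed for these visits.

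On purpose, section I says: "The study is designed to evaluate tolerability and feasibility of the protocol, and guide development of future more definitive doubleblind study". On numbers, section V says: "We will recruit up to 25 subjects, and enrollment will stop once 15 subjects are expected to complete the study". Section VI has 15 subjects receiving the agent.

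**The concern.** Intention to treat normally means that the outcome of every treated subject counts, whatever the adherence. Here non-adherence is itself a reason to stop looking, so the subjects whose later course is least predictable are those with no later data.

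Three features make this more than a matter of labels.

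- **The exit may depend on outcome.** The trial is open label, non-adherence has no threshold, and under section IX the interviewing clinician judges continued participation at each visit from the adverse events. Dosing is flexible, so the line between a permitted reduction and non-adherence is not drawn.
- **Tolerability is an aim.** Hypothesis 1 is tested by the occurrence of moderate or severe adverse events. Section VII lists gastrointestinal effects, which could plausibly lead to missed doses. An exit classed as non-adherence ends adverse-event collection and does not qualify for the two safety follow-up visits.
- **Feasibility is an aim.** Adherence is one of the things the later double-blind study needs to know, and no analysis of it is planned.

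**Working it through.** The plan gives no power calculation, dropout rate, effect size or standard deviation, so there is no figure of its own to reproduce. The check sets the passages together and then gives the scale under stated assumptions.

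**1. What is observed after a non-adherence exit**
- At exit: the final-visit tasks, if the subject agrees to do them.
- After exit: no scheduled rating and no scheduled adverse-event collection. The two follow-up visits are for safety exits; the free visits list no measures.

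**2. What the analysis does with these subjects**
- AISRS, BRIEF, CANTAB: LOCF is stated, so the subject stays in and the last value stands for week 12.
- CGI (Hypothesis 2b) and WASI (Hypothesis 3b): the LOCF sentence names neither.
- BRIEF-A is scheduled only at baseline and at week 12 or drop. If the drop visit is missed, the only value to carry is baseline, which is a change of zero by construction.

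**3. How far the week 12 responder proportion is left open**

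Assume k non-adherence exits among 15 treated, and r responders among the 15 − k observed. The true proportion lies between r/15 and (r + k)/15, a band of width k/15.
- k = 1: 1/15 = 6.7 points
- k = 3: 3/15 = 20 points
- k = 5: 5/15 = 33.3 points

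If all 25 possible recruits were treated, the width would be k/25: 4 points for k = 1 and 12 for k = 3.

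**4. Share of planned observation lost**

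Planned: 15 × 12 = 180 person-weeks. Lost if k subjects leave at week w: k(12 − w)/180.
- k = 3, w = 3: 27/180 = 15%
- k = 3, w = 6: 18/180 = 10%

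**5. Effect on a mean under LOCF (assumed example)**

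Assume that 12 adherent subjects improve by 8 AISRS points, and that 3 removed subjects have a true week 12 change of 0 and a change of x at the exit visit.
- True mean: (12 × 8 + 3 × 0)/15 = 96/15 = 6.4
- LOCF mean: (96 + 3x)/15
- x = 0: 6.4, overstatement 0%
- x = 4: 108/15 = 7.2; 7.2/6.4 = 1.125, overstatement 12.5%
- x = 8: 120/15 = 8.0; 8.0/6.4 = 1.25, overstatement 25%

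The result turns on x and on what happens after exit, and the plan does not observe the second of these.

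**The case against.** The strongest reply is that the plan already says how non-completers enter the analysis. An exit assessment is planned and LOCF carries it forward, so removed subjects are not dropped. That stands for AISRS, BRIEF and CANTAB. A reader might infer that the analysis is intention to treat in name only and follows the adherent subset. The documents do not support this: no completers-only analysis is planned.

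The other replies also have force:
- Feasibility is not lost. Tablets are counted at office visits, weekly calls check adherence, and exits can be counted by reason. Adverse events are recorded up to exit. The information is weakened, not absent.
- With a single arm, intention to treat protects no randomised comparison.
- Hypothesis 2 concerns change while the agent is being taken, so an off-agent rating at week 12 answers a somewhat different question.
- The criterion speaks of study procedures, which is wider than missed doses. A subject who stops attending gives no week 12 rating under any rule.
- Other exit grounds cut off follow-up in the same way, so the gap is not peculiar to non-adherence.

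What remains is that LOCF supplies a value but not the outcome, that it is not stated for CGI or WASI, and that the drop visit is optional. For subjects who would still attend, the gap is avoidable.

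**Conclusion.** The concern holds in a limited form. A mandatory exit without a threshold ends observation of a group that may be selected on response or side effects, and an imputed value replaces a week 12 outcome that could have been collected from willing subjects.

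The size is unknown, because the number of such exits is not given. The k/15 band is arithmetic and assumes only that k subjects have no week 12 observation. The 0% to 25% range rests on the invented example.

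Two larger figures are tempting and should not be used. A flat 25% overstatement describes an analysis of observed week 12 values alone. Under the planned LOCF it arises in the example only if the removed subjects had gained the full 8 points at exit and then lost all of it. Likewise, the recruitment ceiling might suggest that 10 of 25 subjects (40%) will lack a week 12 outcome. That is a ceiling for all causes of exit together, and the 25 may include subjects who fail screening.

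This is a cheap improvement to a small pilot, not a flaw that invalidates it.

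**What to change.** Reconcile four places: the participation sentence at the end of Medication Washout, the early-termination sentence in Safety Assessments, the Study Discontinuation Criteria, and section VI. The aim is that the end of study agent and the end of observation are described separately. Decisions on stopping the agent stay with the investigator; nothing here proposes a change to them.

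- Subjects who are non-adherent to dosing and still willing keep the ratings and adverse-event collection already scheduled through week 12.
- Define the intention-to-treat set as all who received the agent. This also settles whether the denominator is 15 or a larger number.
- Use the observed values in that set in place of carried-forward ones, and state the missing-data rule for CGI and WASI.
- Flag ratings taken off the agent, and show on-agent results as supportive.
- Report non-adherence from the existing tablet counts as a feasibility result, measured against the dose each subject was instructed to take.

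The cost is one amendment, with no new type of visit or test. The downside is that some week 12 values will be off the agent. Subjects who refuse visits are still lost, so some missing data will remain.
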